2.2 Specific Aims

The specific aims of the study will compare the effects of MIST vs. UC on:

• AIM 1: Abstinence as defined by biochemically-verified self-reported 7-day point prevalence abstinence at 6 m (1° study outcome) and 12 m (2° outcome).

- H1: MIST will produce higher abstinence rates.
- AIM 2: Implementation in clinical practice as reflected by: (2a) Patient's selfreported medication adherence at 1, 3 m; (2b) PCP prescription for smoking cessation medication any time after study enrollment, controlling for participant's abstinence; and (2c) whether the prescription is matched to NMR.
 - H2: MIST will produce higher rates of adherence, PCP medication prescription after study enrollment, and NMR-matching of prescriptions.
- AIM 3: A healthcare composite outcome (exploratory) comprised of healthcare utilization visits (ER & hospitalizations) and mortality (all-cause & cause-specific) ascertained via the VUMC EHR, CMS databases, state vital records, and TN HDDS.
 - H3: MIST will reduce health care utilization and death compared to UC.

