Beginning at approximately 3 days and weeks 2, 4, 6, 8, 10, and 12 post-enrollment the participant will receive automated Interactive Voice Response **(IVR) support calls from TelASK** to assess smoking status and medication receipt/adherence. Participants may also opt to speak with a **study Tobacco Treatment Specialist** if needed. At 6 months, all participants (regardless of smoking status) will be offered a second cycle of IVR calls. To maintain the study timeline, participants recruited in the final year of the study will not be offered the second cycle of IVR calls.

3. Outcome ascertainment

At approximately 1-, 3-, 6-, and 12-months participants will complete **follow up surveys** via:

- Text message or email, based on the participant's preference, containing a link to the REDCap follow up survey. If the participant prefers phone contact, a study team member will call. Compensation is \$20 per completed survey. If participants fail to respond to 6, 12 month surveys, they may be contacted by phone call or mailed survey.
- If the participant cannot remotely complete items related to follow up. including surveys, we will make all efforts to coordinate with the patient during any pending appointments at VUMC so they can complete their

survey on a day when they are already scheduled to be at VUMC (e.g. study RA will travel to the One Hundred Oaks clinic of other VUMC clinics to meet participant).

When study staff is unable to reach participants for follow up surveys after several attempts, the next step will be to reach out to alternative contacts provided by the participant at enrollment. An alternative contact that is a reliable close relative (i.e., spouse, significant other, or caregiver) can opt to complete a survey on the participant's behalf as a proxy. This survey will be considered complete "by-proxy" in the study database.

Biochemical Validation of self-reported tobacco abstinence at 6 and 12 months.

• Participants are asked to complete a carbon monoxide (CO) test or salivary cotinine test to confirm quit smoking status if they indicate on the survey that they have quit smoking. \$100 will be offered for completion of biochemical validation at each of the 6 and 12 month timepoints. \$50 will be offered for travel reimbursement at each of the 6 and 12 month timepoints if patients complete biochemical validation in person.

Compensation. Total compensation for full study participation is \$430.00.

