5.11 Retention

Baseline visit: Retention efforts begin at baseline by ensuring that everything possible is done to maximize the likelihood of the participant enjoying the experience of participating in the study. Retention is supported by explaining the informed consent and what may happen in the study, and by collecting complete contact information, including both the address where the participant currently resides as well as multiple contact numbers if available. Participants will be asked to provide contact information for at least one alternative contact who may know their whereabouts if we are ever unable to get in touch with the participant. Alternative contacts can include friends or family members; an alternative contact who is a close relative (ie. spouse, significant other, or caregiver) can opt to be the participant's proxy. Participants will also be asked to provide an email address. The Interactive Voice Response (IVR) that all participants receive beginning 3 days after study enrollment and spanning 3 months also promotes retention through repeated contact via phone, text, or email according to the participant's preferred method of contact.

Additional strategies to promote retention and follow-up: Study participants will be asked to contact the study team if their phone number, address or PCP information changes between study visits; if needed, study staff may assist in re-establishing a primary care provider. The study team may collaborate with the participants PCP by contacting the PCP's clinic staff and/or sending an electronic message through the EHR to the PCP directly to inquire about the status of a patient for follow up on medication adherence, smoking status, or general issues regarding follow up participant contact information. For assessing abstinence, if the participant cannot complete the salivary cotinine test or remote CO monitoring and instead must come into the clinic for the CO breath test, we will make all efforts to coordinate with the patient during any pending appointments at VUMC so that they can take the CO test on a day when they are already scheduled to be at VUMC (e.g., study RA will travel to the One Hundred Oaks clinic or other VUMC clinics to meet participant).

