A secondary outcome is participant self-reported medication adherence assessed at the 1- and 3-month surveys (Aim 2a). Another secondary outcome is PCP prescriptions for smoking cessation medication after study enrollment for participants who continue to smoke. Pharmacy data from CMS will also be used to supplement participant's self-report of whether they received smoking cessation medication prescriptions from their PCP after study enrollment (Aim 2b) and whether the prescriptions were matched to NMR (Aim 2c).

Analysis:

To account for the longitudinal structure of the data with observations at months 1, 3, 6, and 12, Aim 2 analyses will utilize general estimating equations (GEE) with an autoregressive (AR1) correlation structure adjusting for self-reported smoking status and age, race/ethnicity, education, and dependence (baseline FTND score) in a multivariate logistic GEE model. Each of the following three models will estimate a common odds ratio for MIST vs UC for the outcome of interest. All patients will be included in the analyses and missing covariate data will be multiply imputed via predictive mean matching imputation. Standard errors will be estimated via Rubin's rules and statistical significance tested via Wald tests. Unobserved adherence status or prescriptions will be treated as non-adherent or not received, respectively. H2a: We will estimate the odds ratio for being adherent in the 3 months post-enrollment. H2b: We will estimate the odds ratio for receiving a PCP prescription for a smoking cessation medication in the 12 months post-enrollment. PCP prescriptions occurring between any two time points, e.g. months 3 and 6, will be attributed to the latter time point for analysis. H2c: We will estimate the odds ratio for receiving an NMR-

matching PCP prescription. Exploratory and sensitivity analyses: For each of the three outcomes, exploratory analyses will test for interactions between the MIST effect and month of follow up; and for interactions between the MIST effect and medication type (NRT or varenicline). Sensitivity analyses will vary the correlation structure assumptions to ensure the main conclusions are robust to model specifications.

Power:

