The informed consent document will state clearly to patients that the study is being done as a collaboration between VUMC and TelASK, a company that makes automated phone calls. Subjects will be informed that in order to make the phone calls, TelASK will be given information such as their name, study ID, phone number, sex, preference for time of call, and the date that they are discharged from the hospital or enrolled. During the study, TelASK will establish a secure website to view call results in real time, quit status, and "on-demand" counseling requests. Data will be transferred to TelASK via HIPAA-compliant secure FTP. This plan is consistent with what the VUMC IRB has approved for our ongoing NIH funded study of hospitalized smokers (5R01HL11182107: PIs [name] and [name]). Upon completion of the study, data will be transmitted back to VUMC's secure password-protected computer system. All patient data will be purged from TelASK's data files.

Data Security and Confidentiality – Samples

Blood samples used for NMR will be collected and labeled using information such as the study participant number, and/or MRN and stored in a secure location until NMR analysis is conducted by Vanderbilt Pathology Laboratory Services (VPLS), ARUP (currently contracts with VUMC) or other equivalent laboratory.

Blood or saliva for future analyses of genetics and other potentially relevant biological markers will be collected, de-identified, and stored in a secure location, in the laboratory of [name] in Light Hall. Salivary cotinine/CO samples collected for biochemical validation of self reported abstinence will be labelled with study participant number.

| Construct | Measures | Source | Baseline timepoint (CSF, | 1 | 3 | 6 | 12 |
|------------------|--|----------|--------------------------|---|---|---|----|
| | | | RASF, Baseline survey) | m | m | m | m |
| | | | | | | | |
| Sociodemographic | Age, sex, education, race/ethnicity, employment, living | Patient | Х | | | | |
| Factors | situation, health insurance type | | | | | | |
| Medical | Pre-existing condition – VACS [53]; WHI Extension | Patient/ | Х | | | | |
| Condition/Pre- | Study, HIV/AIDS [54] (Coronary heart disease, chronic | EHR/Pr | | | | | |
| existing | obstructive pulmonary disease, stroke, cancer, | оху | | | | | |
| Conditions | hypertension, diabetes, hyperlipidemia) | | | | | | |
| Checklist | Pregnancy | | Х | Х | Х | Х | Х |
| | | | | | | | |

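### Section 9.2 scores every missed 1- or 3-month adherence survey as non-adherent and never tests that rule, although IVR answers from about the same weeks are already collected

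*Combined protocol and SAP*

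**What the plan says.** Section 2.2 places Aim 2a at two times: "medication adherence at 1, 3 m". Section 9.2 agrees: "A secondary outcome is participant self-reported medication adherence assessed at the 1- and 3-month surveys (Aim 2a". Section 5.9 scores each survey by whether medication was taken on at least 5 of the last 7 days. The hypothesis itself is worded as a period: "H2a: We will estimate the odds ratio for being adherent in the 3 months post-enrollment".

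On missing data, section 9.2 multiply imputes covariates only. An adherence status that was not observed is set to non-adherent. The Aim 2 sensitivity analyses change the working correlation and nothing else. Section 9.1, by contrast, tests the corresponding rule for abstinence with odds ratios of 1, 2 and 5 linking loss to follow-up and smoking.

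Section 4.0 schedules IVR calls "Beginning at approximately 3 days and weeks 2, 4, 6, 8, 10, and 12 post-enrollment", and their purpose is "to assess smoking status and medication receipt/adherence". Both arms are covered: section 5.11 refers to "The Interactive Voice Response (IVR) that all participants receive". Section 10.3 adds, for the company making the calls: "Upon completion of the study, data will be transmitted back to VUMC's secure password-protected computer system". Neither section 5.9, Table 2 nor section 9.2 gives these answers a role in any outcome or sensitivity analysis.

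**The concern.** H2a is the patient side of the implementation aim. Under the plan's rule the scored adherence rate in an arm is the response rate multiplied by the adherence rate among responders. Section 5.8 says participants and staff cannot be blinded, so willingness to complete surveys may differ between arms, and the rule would turn such a difference into an apparent adherence effect in either direction.

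The trial holds a second self-report from about the same time that bears on this. Where a participant told the IVR system near week 4 or week 12 that medication was being taken, but did not complete the 1- or 3-month survey, the plan records non-adherence without consulting that answer. It specifies no analysis that would show whether the rule matters.

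**Working it through.** **1. The plan's own figure.** Section 9.2 gives 80% power for 50% versus 59.0% adherence with 1,000 patients. Assuming 500 per arm and a two-sided 5% test, the normal approximation gives 81.6% and exact enumeration with Yates' correction gives 80.5%. The ratios follow: 0.59/0.50 = 1.18, and (0.59/0.41)/(0.50/0.50) = 1.44. The figure reproduces and is not in dispute.

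**2. What the rule does.** Let r be the proportion completing the survey in an arm and a the adherence rate among completers. The scored rate is r × a. If a is the same in both arms, the apparent difference is a × (r_MIST − r_UC). With a = 50% (the plan's UC assumption, used here for completers), each percentage point of difference in response creates 0.5 percentage points of apparent difference in adherence. Producing the whole 9.0-point detectable difference would take a response gap of 9.0/0.5 = 18 points. The rule can shift the estimate; only a large imbalance could create the full effect.

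**3. How many rows an IVR answer could bear on.** Affected rows = P(survey missed) × P(nearby call answered, given missed) × P(use reported, given answered).

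| Input | Range | Source |
|---|---|---|
| Survey missed | 20% | Pilot reached 80% at 6 months (section 3.0); applied to months 1 and 3 by assumption |
| Nearby call answered | 30% to 50% | Assumption |
| Use reported | 30% to 50% | Assumption |

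- Low: 0.20 × 0.30 × 0.30 = 1.8% of survey rows.
- High: 0.20 × 0.50 × 0.50 = 5.0% of survey rows.

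As a share of missing rows alone, this is 0.30 × 0.30 = 9% to 0.50 × 0.50 = 25%.

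**4. Would adding every IVR report to the model sharpen H2a?** Take a correlation that decays with time, in the spirit of the plan's AR(1) structure, at 0.5 to 0.7 between the two surveys, with optimal weighting. Compare two surveys alone with two surveys plus calls; information = 1′R⁻¹1, and the standard error scales as 1/√information.

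| Calls added | Fall in SE, correlation 0.5 | Fall in SE, correlation 0.7 |
|---|---|---|
| Three of weeks 2 to 12 (average over all sets of three) | 2.2% | 1.1% |
| All six of weeks 2 to 12 | 3.8% | 2.1% |
| Weeks 6, 8 and 10 only | 0.5% | 0.1% |

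The value of the IVR data therefore lies in testing the missing-data rule, not in precision.

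**The case against.** **The outcome is consistently defined.** Sections 2.2, 5.9 and 9.2 all put Aim 2a at the 1- and 3-month surveys. The three-month wording of H2a can be read as saying which of the four follow-up times enter the model, as the 12-month wording does for H2b. This stands. A reader might infer that the plan promises a continuous three-month measure and fails to deliver it; the definitions do not support that, and rewording is enough.

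**The interval between surveys is not blank.** A reader might infer that nothing is known about adherence between months 1 and 3. Table 1 collects treatment use since enrollment or the last contact at each survey, and Table 2 names CMS pharmacy records as a source for adherence. Section 9.2 builds neither into H2a, but the data are planned.

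**The IVR answer may not be equivalent.** The documents give no item wording, recall window or response rate for the calls. The item may be a simple yes/no that cannot be scored as 5 of 7 days. Surveys may be pursued through about 24 call attempts over 4 to 8 weeks (section 5.9), and section 6.1 counts the calls from discharge or randomization while section 4.0 counts from enrollment, so a call and its survey may be weeks apart. A report of use on one need not contradict non-use on the other. This stands, and it is why IVR answers should not simply replace the main outcome.

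**Few rows may end up missing.** Phone, mail, proxy and health-record routes come first. This also stands and could lower the 20% input.

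**IVR is treatment support, not outcome ascertainment.** Section 4.0 does separate the two. That justifies leaving IVR out of the main analysis, but not leaving the missing-data rule untested.

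**Conclusion.** The point holds in a narrow form. Section 9.2 fixes every missing 1- or 3-month adherence status as non-adherent, offers no sensitivity analysis of that choice, and overlooks reports collected at about the same times in both arms. In an unblinded trial that is an avoidable route to bias in a secondary outcome.

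The 1.8% to 5.0% of rows is an illustration: the 20% is borrowed from a different time point in the pilot, and the other two ranges are not in the documents. The direction of any bias is unknown, because no response rates by arm are given.

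A reader might also infer a material loss of precision from using only two surveys. Under decaying correlation the loss is about 1% to 4% of the standard error, and the mid-interval calls contribute 0.5% or less. Larger gains appear only if correlation is taken as constant over time (5% to 13% at the same correlations), which is not the structure the plan specifies. The primary outcome and the stated H2a power are unaffected.

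**What to change.** In section 9.2:

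- Keep the 1- and 3-month surveys as the main H2a outcome, and reword H2a as adherence at months 1 and 3.
- Add one pre-specified analysis. A missing survey takes the IVR adherence answer nearest in time (about week 4 or week 12), where one exists and its item can be mapped to the 5-of-7-day rule. Only then does the non-adherent default apply. State the mapping and the largest allowed gap in days before the data are examined.
- Report it beside the survey-only result, with survey and call response by arm.
- Optionally, as exploratory work, fit a GEE to all survey and IVR reports, with terms for time and mode, a correlation structure that respects unequal spacing, and unanswered calls left missing rather than scored non-adherent.

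The cost is SAP wording and a data merge, with no new participant contact. The downside is that IVR answers are automated, come from self-selected responders and have undocumented wording. If the item cannot be mapped, the plan should say so and test the default in another way, for example with a range of odds ratios as section 9.1 does for abstinence.

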9.0 Statistical Considerations

9.1 Aim 1

The primary study outcome is biochemically-verified self-reported 7-day point prevalence abstinence at 6 months as defined by salivary cotinine level < 10 ng/ml or expired CO <10 ppm. A secondary outcome is biochemically-verified self-reported 7-day point prevalence abstinence at 12 months. Brief surveys will be conducted at 6 and 12 months after study enrollment to determine self-reported abstinence. Biochemical validation of smoking status is accomplished via mailed salivary cotinine samples or expired CO.

Analysis:

The effect of MIST vs. UC on biochemically-verified abstinence at 6 months will be estimated via a relative risk of abstinence and tested at a 5% significance level via a chi-squared test with Yates' continuity correction. The same method will be applied

to the secondary outcome at 12 months. Anticipated loss to follow up is accounted for in the expected approximate UC abstinence rates where persons lost to follow up will be treated as non-abstinent. However, sensitivity analyses will consider a range of possible odds ratios (1, 2, and 5) linking loss to follow-up and smoking. [51] Exploratory analyses testing for effect heterogeneity will use multivariate logistic regression models adjusting for the main effect of a potential modifier and testing for an interaction with the effect of MIST. The potential effect modifiers to be explored are age, race, sex, NMR, and pre-intervention plan to quit.

Power:

Conservatively assuming a biochemically validated abstinence rate of 10% under UC, a chi-squared test on 1000 patients (at 6 months) will detect a MIST abstinence rate of 16.2% (Risk Difference=6.2%, Relative Risk=1.62, Odds Ratio=1.74) with 80% power. Assuming a 15% biochemically validated abstinence rate under UC (at 12 months), a 22.2% rate under MIST (RD=7.2%, RR=1.48, OR=1.62) is detectable with 80% power. Power was estimated via simulating 20K datasets under the settings above in the statistical program R and were checked against the simplified estimates of the pwr package.

9.2 Aim 2

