For all hypotheses related to clinical implementation, we conservatively estimate power by focusing on the first observation time point. Under a common odds ratio, power will be higher when analyzing all time points together. H2a: Assuming a selfreported adherence rate of 50% under UC, analysis of 1000 patients (at 3 months) will detect a MIST adherence rate of 59.0% (Risk Difference=9.0%, Relative Risk=1.18, Odds Ratio=1.44) with 80% power. H2b: Because self-reported abstinence at a given time point will be a very strong predictor of not receiving a PCP prescription for smoking cessation medication at the following time point, with regard to statistical power the sample sizes will be effectively reduced by the respective quit rates. For this effective sample size reduction, we conservatively assume guit rates of 15% for UC and 25% for MIST. Assuming a PCP prescription rate of 30% under UC, a 39.8% rate under MIST (RD=9.8%, RR=1.33, OR=1.54) is detectable with 80% power. H2c: Similarly, assuming an NMR-matching PCP prescription rate of 15% under UC, a 23.2% rate under MIST (RD=8.2%, RR=1.55, OR=1.71) is detectable with 80% power. Power was estimated via simulating 20K datasets under the settings above in the statistical program R and were checked against the simplified estimates of the pwr package.

9.3 Aim 3

Passive surveillance of 12-month clinical composite outcomes (ER visit, hospitalization, or death) in VUMC and non-VUMC facilities is also conducted by specific members of the research team.

Analysis:

The effect of MIST vs UC on the Aim 3 primary outcome of a healthcare composite outcome consisting of hospitalization, emergency department visit, and/or death within 12 months will be estimated via a relative risk of the composite outcome and tested at a 5% significance level via a Chi-squared test with Yates' continuity correction. The same method will be applied to the secondary outcomes of hospitalization, ED visit, and mortality analyzed separately. Exploratory analyses testing for effect heterogeneity will use multivariate logistic regression models adjusting for the main effect of a potential modifier and testing for an interaction with the effect of MIST. The same modifiers as in Aim 1 will be tested. All analyses will be reported as primary, secondary, or exploratory as specified here.

Power:

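### The Aim 2 GEE models list no month term: the common odds ratios are slightly attenuated, and the exploratory MIST-by-month model is left under-specified

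*Combined protocol and SAP*

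**What the plan says.** Section 9.2 sets up a longitudinal analysis: "To account for the longitudinal structure of the data with observations at months 1, 3, 6, and 12". It chooses a logistic GEE with AR1 working correlation, "adjusting for self-reported smoking status and age, race/ethnicity, education, and dependence (baseline FTND score) in a multivariate logistic GEE model". The target is a single effect per outcome: "Each of the following three models will estimate a common odds ratio for MIST vs UC for the outcome of interest". H2a covers the 1- and 3-month surveys ("We will estimate the odds ratio for being adherent in the 3 months post-enrollment"). H2b runs over 12 months, and a prescription between two time points is counted at the later one, so the windows are 1, 2, 3 and 6 months long. H2c uses the same framework for NMR-matched prescriptions. Missing outcomes are filled in: "Unobserved adherence status or prescriptions will be treated as non-adherent or not received, respectively".

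The section then says that "exploratory analyses will test for interactions between the MIST effect and month of follow up", without writing out that model. For Aim 1, Section 9.1 describes its interaction models as "adjusting for the main effect of a potential modifier and testing for an interaction with the effect of MIST", and Section 9.3 does the same for Aim 3. Section 9.2 has no such statement.

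**The concern.** AR1 describes how a participant's observations are correlated. It does not let the mean differ from one month to the next. An odds ratio common to the months belongs to a model in which each month has its own baseline odds, and the listed covariates do not provide that.

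Equal rates across months are unlikely. For prescriptions the windows are of unequal length, so even constant monthly prescribing gives unequal proportions. For adherence, non-response counts as non-adherence, so any rise in non-response between the two surveys adds a downward trend.

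Two things are at stake. One is the size of the reported H2a to H2c odds ratios. The other is the planned check that the effect of MIST is constant over follow-up, which supports the common-odds-ratio reading.

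**Working it through.** **Inputs.** From Section 9.2: 1000 participants; H2a 50% vs 59.0% (OR 1.44); H2b 30% vs 39.8% (OR 1.54), with assumed quit rates of 15% and 25%; H2c 15% vs 23.2% (OR 1.71). Assumed here: 1:1 allocation, two-sided 5% for Aim 2, the month-specific rates, and the within-person correlation. The plan gives no rates by month.

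**1. The plan's own figures.** For H2a ("analysis of 1000 patients (at 3 months) will detect a MIST adherence rate of 59.0"), the pooled rate is 0.545.
- Null SE = √(2 × 0.545 × 0.455/500) = 0.0315.
- Alternative SE = √((0.25 + 0.59 × 0.41)/500) = 0.0314.
- z = (0.09 − 1.96 × 0.0315)/0.0314 = 0.90, so power is 81.6% (80.7% simulated with Yates' correction).

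H2b and H2c use 500 × 0.85 = 425 and 500 × 0.75 = 375 participants. They give 82.9% and 84.0% by formula, and 81.6% and 81.4% with Yates' correction. The plan's 80% is reproduced.

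**2. Attenuation without month.** Hold the odds ratio constant at every month. The MIST rate is OR × odds/(1 + OR × odds). Average each arm over months, then take the odds ratio of the averages. This works because every participant has a row at each month.

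Worked case, H2a with UC 50% then 40%:
- MIST rates are 0.5902 and 0.4898, mean 0.5400. The UC mean is 0.45.
- Pooled OR = (0.5400/0.4600)/(0.45/0.55) = 1.435.

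| Outcome, true OR | Assumed UC rates by month | OR without month |
|---|---|---|
| H2a, 1.44 | 50%, 50% | 1.44 |
| H2a, 1.44 | 50%, 40% | 1.435 |
| H2a, 1.44 | 50%, 30% | 1.42 |
| H2b, 1.54 | 30, 20, 15, 15% | 1.52 |
| H2b, 1.54 | constant 2% per month: 2, 4, 6, 11% | 1.52 |
| H2b, 1.54 | constant 5% per month: 5, 10, 14, 26% | 1.50 |
| H2c, 1.71 | 15, 10, 8, 5% | 1.69 |

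The constant-rate rows use 1 − (1 − r)^k with k = 1, 2, 3, 6. Larger shifts need steeper trends: H2b gives 1.49 for 30, 15, 10, 5%; H2a gives 1.38 for 70% then 35%, and 1.32 for 80% then 30%.

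**3. The main test.** In simulated GEE fits (AR1, robust SE, 1000 participants), H2a with 50% then 30% and OR 1.44 had power 93.3% without month and 93.4% with it. With no MIST effect, rejection was 4.8% vs 4.9% for that trend, and 6.4% vs 6.7% for 50% then 40%. H2b with rates 30, 20, 15, 10% and no effect gave 5.8% both ways. With month in the model, the odds ratio returned to its true value to within simulation error.

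**4. The interaction test, if month has no main effect.** Take logit p = a + b·MIST + c·MIST·(month 3). UC has one logit for both surveys, and MIST has a separate one for each. So c estimates logit(MIST rate, month 3) − logit(MIST rate, month 1), which is the time trend within the MIST arm. Suppose MIST has no effect and adherence falls from 55% to 50% in both arms:
- c = logit(0.50) − logit(0.55) = −0.201, although the true interaction is 0.
- With 500 in the arm and within-person correlation φ, the variance is 1/(500 × 0.2475) + 1/(500 × 0.25) − 2φ/(500 × √(0.2475 × 0.25)).
- φ = 0.2: SE 0.113, z = 1.77, rejection 42%.
- φ = 1/3: SE 0.104, z = 1.94, rejection 49%.

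For 60% to 50%, c = −0.405. Rejection is 94% (φ = 0.2, SE 0.114) and 97% (φ = 1/3, SE 0.104). Simulated GEE fits agree: 42% to 51% for the 5-point change and 95% to 98% for the 10-point change. With a month main effect the simulated rate was 5% to 6%. If rates are flat, the test without month rejects at about 5%, so there is no error.

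**The case against.** The strongest reply is that the false interaction belongs to a model that the plan never specifies. Section 9.2 says only that the interaction will be tested. The same sentence plans a MIST-by-medication-type interaction, and medication type is not on the covariate list either, so the list evidently does not define the interaction models. Where the protocol does describe such models, in Sections 9.1 and 9.3, it includes the modifier's main effect. The test is also exploratory. All of this stands. A reader might infer that the planned test will report an interaction that is not there, but the documents do not support that. They support only that the model is unspecified and that one literal reading of it fails.

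A second reply is that the attenuation is small and harmless to inference. That stands too. Month is balanced across arms, so this is not confounding; odds ratios simply do not average across months. A reader might infer that the H2a to H2c effects are seriously understated. That needs trends such as 70% to 35% or 80% to 30%, neither of which contains the plan's 50% UC adherence rate.

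A third reply is that self-reported smoking status, if updated at each survey, could carry part of the trend. The section does not say whether it is updated. The simulations above left it out. In separate runs with time-varying smoking status (assumed log OR −1 or −2, prevalence 60% to 70% or the reverse) and adherence falling from 60% to 50%, the test without month still rejected in 65% to 100% of trials. This reply therefore reduces the problem in some settings and does not remove it.

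**Conclusion.** The omission is real and its effect on the main Aim 2 results is small. For a constant true effect, the models as listed give about 1.42 to 1.435 instead of 1.44 for H2a and about 1.50 to 1.52 instead of 1.54 for H2b, under moderate trends that are assumed here. The validity and power of the main test are practically unaffected.

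The more useful reason to act is the exploratory MIST-by-month test. Run on the listed covariates alone, it would falsely reject about 40-50% of the time for a 5-point change in adherence and over 90% for a 10-point change, against about 5% with a month main effect. Those rates are conditional on that literal reading, on the assumed trends and on the within-person correlation. They do not mean that every outcome that changes over time would produce a rejection. No primary or secondary conclusion rests on this test.

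**What to change.** In Section 9.2, add month of follow-up as a categorical main effect to all Aim 2 GEE models, with 2 levels for H2a and 4 for H2b and H2c. State that the MIST-by-month model contains this main effect, as Sections 9.1 and 9.3 already do for their modifiers.

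The cost is a line or two of wording and at most three extra parameters with about 1000 participants. No new data are needed and there is no loss of power. Writing it down in advance also removes a modelling choice that would otherwise be made after the data are seen.
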